2.4.2 Prior, concomitant and post therapies

Regarding the prior treatment for advanced breast cancer, the number, type, setting and best response of regimes before study were evaluated. The type was classified by WHO ATC level 2 and preferred name. Radiotherapies and surgeries were analysed similarly.

Concomitant medications and significant non-drug therapies prior to and after the start of the study drug will be coded according to the WHO Drug Reference List and summarized by ATC class and preferred term using frequency distributions.

2.5 Analysis of the primary objective

2.5.1 Primary endpoint

The primary objective of this study was the assessment of the clinical benefit rate after 24 weeks.

The **Clinical Benefit Rate (CBR)** is the proportion of patients with a best overall response of confirmed complete (CR) or partial (PR) response or stable disease (SD) or non-complete response, non-progressive disease (NCRNPD) within Week 24. The best overall response for

each patient is determined from the sequence of investigator overall lesion responses until week 24 according to RECIST 1.1. To be assigned a best overall response of CR at least two determinations of CR at least 4 weeks apart before progression are required. To be assigned a best overall response of PR at least two determinations of PR or better at least 4 weeks apart before progression (and not qualifying for a CR) are required. To be assigned a stable disease, two determinations of SD at least 12 weeks apart (and not qualifying for PR or CR) are required.

Patients with best overall response “unknown” will be summarized by reason for having unknown status. The following reasons will be used:

- No valid post-baseline assessment
- All post-baseline assessments have overall response UNK
- New anti-neoplastic therapy started before first post-baseline assessment
- SD too early (≤ 6 weeks after randomization)
- PD too late (>12 weeks after randomization and not qualifying for CR, PR, or SD)

Special (and rare) cases where BOR is unknown due to both early SD and late PD will be classified as “SD too early”

During data review. i.e. before analysis, the number and reasons for best responses falling into the category “unknown” according to RECIST 1.1 criteria are investigated. In addition, the impact of confirmation of response on the outcome in the context of the visit schedule and assessment timepoints will be assessed. If necessary, further sensitivity analyses were defined to adjust for this uninformative category.

Any discontinuation due to ‘Disease progression’ without documentation of progression by RECIST criteria will be carefully reviewed during the data review meeting. Only patients with documented deterioration of symptoms indicative of progression of disease should have this reason for discontinuation of treatment or study evaluation.

Per RECIST 1.1, a change in methodology can be defined as either a change in contrast use (e.g. keeping the same technique, like CT, but switching from with to without contrast use or vice-versa, regardless of the justification for the change) or a change in technique (e.g. from CT to MRI, or vice-versa), or a change in any other imaging modality. A change in methodology will result by default in an UNK (unknown) overall lesion response assessment. However, another response assessment than the Novartis calculated UNK response may be accepted from the investigator or the central blinded reviewer if a definitive response assessment can be justified based on the available information. Potential discrepancies between the modality used and overall lesion response (e.g. change in modality but response is different from ‘Unknown’) will be queried during the data validation process.”

Additionally, the CBR at EOT was determined.

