7.1 Study flow and visit schedule

Table 7-1 lists all of the assessments and indicates with an “X”, the visits when they are performed. All data obtained from these assessments must be supported in the patient’s source documentation.

Table 7-1 Visit evaluation schedule

	Screening/ Baseline Day -21 to C1D1	Cycle 1 Day 1	Cycle 1 Day 15 (+/- 3d)	Cycle 2 Day 1 (+/- 3d)	Cycle 2 Day 15 (+/- 3d)	Cycle 3 Day 1 (+/- 3d)	Cycle 5 Day 1 (+/- 3d)	Cycle 6 Day 1 (+/- 3d)	Cycle 7 Day 1 (+/- 3d)	Further cycles (+/- 3d)	Sympt omatic Progre ss ¹⁰	EOT	Follo w up	P&S Follow Up
Hematology, Biochemistry ⁸ Please document if clinically indicated/significant	X (fasting)	(X)*	X	X	X	X	X	X	X	X	X	X		
ECG ⁹	X (D-7 to -1) (anytime)		X (anytime)	X (anytime)	X (anytime)	X (anytime)	X (anytime)	X (anytime)				X (anytime)		
Urinalysis, Serum Lipid Profile, INR ⁸	X (fasting)													
Continuation of protocol														
Tumor evaluation: CT for chest, abdomen, pelvis	X ¹								X	(every 12 weeks)	X	(X) ^{2,5}		(X) ^{2,5}
Tumor evaluation: CT / MRI for Brain if clinically indicated	(X) ¹								(X) ²	(every 12 weeks) ²	(X) ²	(X) ^{2,5}		(X) ^{2,5}
Tumor evaluation: Bone Scan	X ³													
Tumor evaluation: Bone X-Ray / Bone CT, Skin lesion photography	(X) ⁴								(X) ⁴	(every 12 weeks) ⁴	(X) ⁴	(X) ^{2,5}		(X) ^{2,5}
Ribociclib/ letrozole (and goserelin) Dosing		Continuation of protocol												
Patient Diary		X		X		X								
EORTC QLQ-C30 & module BR-23		X		X		X								
Progression / survival status ⁷														P&S ⁷ X

Note: 1 Cycle = 28 days

*not necessary if last assessment was within 7 days before first intake of study medication.

§if EOT occurs for other reason than progression and patient withdraws consent for PFS follow up, if last tumor evaluation is older than 12 weeks.

¹Existing radiologic assessments can be used if assessed up to 28 days prior to C1D1. A corresponding RECIST evaluation should be performed and documented.

²If findings at baseline evaluation.

³Existing bone scans can be used if assessed up to 56 days prior to C1D1.

⁴Positive areas on bone scans must be assessed by X-ray or CT scan with bone windows on screening/baseline and should continue to be assessed using the same modality. (X-ray or CT scan with bone windows) every 12 weeks. Not all positive areas need to be followed up (non-target lesions) if significant and relevant tumor burden can be assessed by CT.

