7.2 Assessment types

7.2.1 Efficacy assessments

Tumor assessment and response will be evaluated according to RECIST (Version 1.1) (Protocol Post-text Supplement: 1). All radiologic assessments must be performed within a +/- 7 day window of the visit.

Patients should have either at least one lesion that can be measured as per RECIST criteria OR have bone lesions: lytic or mixed (lytic + sclerotic) in the absence of measurable disease OR have non-measurable disease.

For patients with measurable disease at screening (as per RECIST criteria), tumor progression will be evaluated every 12 weeks until progression or End of study, whichever is first (according to the RECIST 1.1 criteria). All tumor evaluations performed routinely in addition to the above mentioned will be evaluated and documented according to RECIST 1.1 as well. All patients being discontinued from the study for disease progression must have their progression documented using the criteria specified in RECIST 1.1.

Bone scans must be performed at screening within 56 days before C1D1. Positive areas on bone scans must be assessed by X-ray or CT scan with bone windows, prior to C1D1 and should continue to be assessed using the same modality (X-ray or CT scan) every 12 weeks until progression or End of study. Additional bone scans should be performed if clinically indicated. Abnormalities found on subsequent bone scans must be confirmed by X-ray or CT scan. Bone scans may be replaced by whole body CT, provided that this is local standard. The whole-body CT must be performed within a +/- 7 days window of the visit.

Color photography, including a metric ruler to estimate the size of the lesion, must be acquired for all skin lesions present at baseline. These should be followed throughout the study according to the schedule outlined in Table 7-1.

All patients being discontinued from the study for other reasons than tumor progression (or death) should be scheduled for tumor evaluation at 12 week intervals after discontinuation until LPLV occurs.

The same method of assessment and the same technique should be used to characterize each identified and reported lesion at baseline for each study tumor assessment after start of study treatment.

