- PR = at least two determinations of PR or better at least 4 weeks apart before progression (and not qualifying for a CR) where confirmation required or one determination of PR prior to progression where confirmation not required.
- SD = at least one SD assessment (or better) > 6 weeks after randomization/start of treatment (and not qualifying for CR or PR).
- PD = progression ≤ 12 weeks after randomization/ start of treatment (and not qualifying for CR, PR or SD).
- UNK = all other cases (i.e. not qualifying for confirmed CR or PR and without SD after more than 6 weeks or early progression within the first 12 weeks).

Overall lesion responses of CR must stay the same until progression sets in, with the exception of a UNK status. A patient who had a CR cannot subsequently have a lower status other than a PD, e.g. PR or SD, as this would imply a progression based on one or more lesions reappearing, in which case the status would become a PD.

Once an overall lesion response of PR is observed (which may have to be a confirmed PR depending on the study) this assignment must stay the same or improve over time until progression sets in, with the exception of an UNK status. However, in studies where confirmation of response is required, if a patient has a single PR ($\geq 30\%$ reduction of tumor burden compared to baseline) at one assessment, followed by a $< 30\%$ reduction from baseline at the next assessment (but not $\geq 20\%$ increase from previous smallest sum), the objective status at that assessment should be SD. Once a confirmed PR was seen, the overall lesion response should be considered PR (or UNK) until progression is documented or the lesions totally disappear in which case a CR assignment is applicable. In studies where confirmation of response is not required after a single PR the overall lesion response should still be considered PR (or UNK) until progression is documented or the lesion totally disappears in which case a CR assignment is applicable.

Example: In a case where confirmation of response is required the sum of lesion diameters is 200 mm at baseline and then 140 mm - 150 mm - 140 mm - 160 mm - 160 mm at the subsequent visits. Assuming that non-target lesions did not progress, the overall lesion response would be PR - SD - PR - PR - PR. The second assessment with 140 mm confirms the PR for this patient. All subsequent assessments are considered PR even if tumor

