5.1 Definition of efficacy variables

Progression:

1. ds.eotdreasn = 4 (Main reason for ribociclib discontinuation = progressive disease)
2. ds.eotprdi1n = 1 (Radiologic progression according to RECIST 1.1) OR
3. ds.eotprdi3n = 1 (Clinically symptomatic progress) OR
4. zr.recoveran = 4 (Overall lesion response = Progressive Disease) OR
5. zr.recnewln=1 (New Lesion)

Progression date:

1. ds.eotcprdt (date of clinically symptomatic progress) OR
2. Date of Evaluation where zr.recoveran = 4 or zr.recnewln = 1

Response:

3. zr.recoveran (Overall lesion response)

Assessment Date:

4. zr.tlesdt (Date of image or examination, Target Lesion Assessment)
5. zr.ntlesdt (Date of image or examination, Non-Target Lesion Assessment)
6. zr.nlesdt (Date of image or examination at which new lesion appeared)

Date of Death:

7. sc.deathdt

Date of last contact:

8. sc.eoslcdt

Start of treatment = first administration of Ribociclib or Letrozole:

9. min(min(zq.ribostdt), min(zq.letrstdt))

5.1.1 Clinical Benefit Rate (CBR) until week 24

Best overall response in (CR, PR, SD, NCRNPD):

1. zr.recoveran = 1; at least two determinations of CR at least 4 weeks apart before progression OR
2. zr.recoveran = 2; at least two determinations of PR or better at least 4 weeks apart before progression (and not qualifying for a CR)
3. zr.recoveran = 3; two determinations of SD at least 12 weeks apart (and not qualifying for PR or PD)

4. zr.recoveran = 5

Tumor evaluations are scheduled for baseline, Cycle 4 and cycle 7 etc. (every 12 weeks). Thus, to assess the CBR at week 24 the first two post-baseline evaluations have to be considered. Additionally it has to be checked that no progression occurred during the following 4 weeks. Deviations against the time schedule is investigated and assessed during the data review meeting.

5.1.2 Overall response rate (ORR) by week 24

Similar to 5.1.1, but the best overall response must be in in (CR, PR)

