5.3 Programming rules

5.3.1 Calculation of ‘time to event’ variables

Time to event = end date - start date + 1 (in days).

When no post-baseline tumor assessments was available, the date of first application of treatment was used as end date (duration = 1 day) when time was to be censored at last tumor assessment, i.e. time to event variables can never be negative.

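### Best response PD is cut off at 12 weeks, the nominal date of the first scan, so some documented progressions are reported as 'unknown'

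*SAP*

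**What the plan says.** Protocol Appendix 2, section 3.1, defines the category as "PD = progression ≤ 12 weeks after randomization/ start of treatment (and not qualifying for CR, PR or SD". What is left over goes to unknown: "UNK = all other cases (i.e. not qualifying for confirmed CR or PR and without SD after more than 6 weeks". Protocol 10.4.1 refers to this appendix for details of the primary variable.

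SAP 2.5.1 carries the same limit into its list of reasons for an unknown best response: "PD too late (>12 weeks after randomization and not qualifying for CR, PR, or SD".

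For SD, protocol 10.4.1 and SAP 2.5.1 set a study-specific rule: SD must be seen twice, with 12 weeks or more between the two assessments.

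On timing, SAP 5.1.1 says "Tumor evaluations are scheduled for baseline, Cycle 4 and cycle 7 etc. (every 12 weeks". The footnotes to protocol Table 7-1 give "Note: 1 Cycle = 28 days", and protocol 7.2.1 says "All radiologic assessments must be performed within a +/- 7 day window of the visit".

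SAP 2.5.2 tabulates PD and unknown as separate response categories, each with an exact 95% confidence interval, alongside the CBR. SAP 2.5.1 also has the unknowns broken down by reason and examined at data review, with sensitivity analyses if they are judged necessary.

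**The concern.** The 12-week limit comes from a generic guideline and was not matched to this trial's 12-weekly scans. Two kinds of patient with documented RECIST progression then land in the unknown row:

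- a patient whose first scan shows progression but was taken after the limit, although still inside the permitted window;
- a patient with SD at the first scan and progression at the second, who fails the two-assessment SD rule and is too late for PD.

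At stake is the reading of the primary response table. The PD row would be too small. The unknown row, which a reader takes to mean missing or unevaluable data, would be too large and would contain known treatment failures. The SAP itself describes unknown as uninformative, which documented progression is not.

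**Working it through.** The documents give no expected share of unknowns, so there is no stated figure to reproduce. The check sets the limit against the scan dates.

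**1. Position of the limit.** Cycle length is 28 days (protocol Table 7-1) and the first scan is at Cycle 4 (SAP 5.1.1). C4D1 is 3 × 28 = 84 days after C1D1. The limit is 12 × 7 = 84 days. The two coincide.

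**2. Permitted window.** 84 ± 7 gives 77 to 91 elapsed days, which is 15 possible days. Of these, 85 to 91 (7 days) lie beyond the limit. If the SAP 5.3.1 day count, "Time to event = end date - start date + 1 (in days", is applied, a scan exactly on C4D1 counts as day 85, so 8 of the 15 days lie beyond it. The SAP states that count for time-to-event variables and does not say whether it governs the 12-week limit.

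**3. Share of in-window first-scan progressions classed as unknown.** The documents do not give the distribution of actual scan dates. Each row below is therefore an assumption.

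| Assumed scan timing | Elapsed days | With +1 day |
|---|---|---|
| Uniform over the window | 7/15 = 47% | 8/15 = 53% |
| Bell-shaped around C4D1, SD 3 days | 43% | 57% |
| Bell-shaped around C4D1, SD 2 days | 40% | 60% |
| PD dated at the earliest of two independent uniform dates | (7/15)² = 22% | (8/15)² = 28% |
| PD dated at the earliest of three | (7/15)³ = 10% | (8/15)³ = 15% |
| All exactly on C4D1 | 0% | 100% |
| All 1-7 days early | 0% | 0% |
| All 1-7 days late | 100% | 100% |

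The two earliest-date rows reflect protocol Appendix 2, section 3.2.7, which dates a progression at the earliest image of that evaluation.

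**4. SD, then PD.** Take a patient with SD at week 12 and PD at week 24, on scheduled scans. There is one SD assessment, so the two-assessment rule fails. Progression is at about 168 days (6 × 28), past 84, so the PD rule fails. There is no CR or PR. The remainder category applies and the patient is unknown. This does not depend on where in the window either scan fell.

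**5. Effect on the CBR.** The numerator is CR + PR + SD + NCRNPD. Neither PD nor unknown is in it. Moving a patient between those two rows changes neither the numerator nor the FAS denominator.

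**The case against.** The best defence is that nothing of consequence moves. PD and unknown are both non-benefit, so the CBR is the same. PFS in SAP 2.7.2 uses the first documented progression with no 12-week limit. The late progressions are visible too: they have their own line in the by-reason breakdown, and a reader could add that line back to PD. Data review looks at the unknowns before analysis. This stands as far as it goes, and it confines the point to the PD and unknown rows. It does not remove the defect, because these steps reveal the misclassification but leave the rule, and both reported rows, as they are.

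A second defence is that the generic SD rule in Appendix 2 section 3.1, a single SD more than 6 weeks after start, would make the SD-then-PD patient SD. The SAP's own reason for SD seen too early echoes that rule. But protocol 10.4.1 and SAP 2.5.1 both require two assessments for this endpoint, and under that rule the patient is unknown. The 12-week PD limit was designed to sit beside the single-assessment SD rule, and only the SD half was changed.

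A reader might infer stronger things that the documents do not support:

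- **That about half of first-scan progressions are lost.** That needs scan dates spread symmetrically around C4D1. The documents give no distribution, and the earliest-image rule alone could lower the share to 10-28%.
- **A patient count from the phase Ib PD rates.** These are 3/28 and 4/19 patients. That study's scan schedule and PD rule are not described here, the pretreated rate does not fit the untreated women in cohort B1, and protocol 7.2.1 also has additional routine tumor evaluations documented by RECIST, so some progression may be recorded earlier.
- **That the CBR will be inflated.** No section says unknowns will be dropped. SAP 2.5.3 keeps them in the denominator as non-responders, although it says so only for the ORR.

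**Conclusion.** The plan is wrong as written on this point. Followed literally, it places documented RECIST progression in the unknown row by two routes, one dependent on scan timing and one not. PD is understated and unknown overstated in the primary response table; the CBR on the FAS is unaffected.

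The size of the first route cannot be fixed from the documents. It is 47% of in-window first-scan progressions (53% with the +1 day count) under uniform scan dates, about 10-28% if PD takes the earliest of two or three independently timed images, and anywhere from 0 to 100% at the extremes. The second route takes every patient with SD at week 12 and PD at week 24. Its number is not predictable from the documents either. The reasoning assumes that start of treatment coincides with C1D1 and that the study-specific two-assessment SD rule governs.

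**What to change.** For the week-24 tables:

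1. Define best response PD as RECIST progression from start of treatment up to and including the week-24 evaluation and its +7-day window (6 × 28 + 7 = 175 elapsed days), in patients without a qualifying CR, PR, SD or NCRNPD. State the day count used.
2. Anchor the rule to start of treatment. SAP 2.5.1 counts from randomization, which SAP 1.1 says did not take place.
3. Remove lateness of PD as a reason for unknown when progression falls within that period.
4. Keep unknown for patients with neither a qualifying response nor documented progression by then. This includes a patient with a single SD and no later evaluable scan, who needs a reason code of their own.
5. State that unknowns stay in the CBR denominator as non-benefit.
6. List the departure from protocol Appendix 2 in SAP section 4.

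Merely moving the limit to 13 weeks is not enough. With a 91-day limit and the +1 day count, the last day of the window (day 92) is still missed, which is 1/15 = 7% under uniform dates, and the SD-then-PD patients stay unknown.

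The cost is SAP wording and a small programming change. No new data are needed.

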2.5.2 Statistical hypothesis, model, and method of analysis

In this single-arm trial, the primary objective is to estimate the CBR. Therefore, no statistical hypothesis or model is underlying the analysis.

The CBR (best overall response of CR or PR or SD or NCRNPD) as well as individual response categories (CR, PR, SD, PD, NCRNPD or unknown) will be summarized using frequency tables together with their associated two-sided exact 95% confidence intervals (Clopper-Pearson method).

The Full Analysis Set will be used for the primary efficacy analysis, the per-protocol set will serve as sensitivity analysis. Further, selected analysis tables (see RAP module 7.1) were displayed as sensitivity analysis for a modified FAS population which excludes patients from centers with a relevant inspection finding.

2.5.3 Handling of missing values/censoring/discontinuations

Since the definition of the primary variable was derived from tumor assessments based on RECIST 1.1 criteria, these criteria apply for the handling of missing values in tumor assessments. The evaluation of overall lesion response at each assessment is a composite of the target lesion response, non-target lesion response and presence of new lesions (see protocol, Post-text supplement 1). If the evaluation of any of the target or non-target lesions identified at baseline could not be made during follow-up, the overall status must be 'unknown' unless progression was seen. Patients with a best overall response assessment of unknown (UNK) were not be regarded as 'responders' but were included in the denominator for the calculation of the ORR for the FAS.

For patients who took other anti-neoplastic drugs their efficacy data will be censored so that the tumor assessments made after the administration of the other anti-neoplastic drugs are not included in the primary efficacy analyses. Sensitivity analysis including these observations may be performed if decided during data review meeting.

2.5.4 Supportive analyses

CBR until Week 24 were additionally presented for the Per-protocol Set (PPS). Furthermore, the CBR were summarized by subgroups (cohorts A, B, B1 and B2) for the FAS and PPS, respectively.

2.5.4.1 Time to response (CR or PR)

Furthermore, the time to overall response (CR or PR) were analyzed by Kaplan Meier curve and Kaplan meier statistics for the total population and for cohorts. The time to overall response is the time between date of start of treatment until first documented response (CR or PR). Patients who did not achieve a confirmed PR or CR will be censored:

- At maximum follow-up (i.e. FPFV to LPLV used for analysis) for patients who had a PFS event (i.e. either progressed or died due to any cause)

